Before treatment, there will be a 4 week observation-only period, and another one 8 weeks post-treatment, so that the total study period will be 6 months.

We aim for 20 patients to be included in this study.

see more detailed graphics in the next section

In terms of ancillary, laboratory-based studies, we intend to draw blood before treatment and at the 45-, 75-, 105- and 135-day of treatment time-points. We will measure cytokine/chemokine/lipid pain- and inflammation markers in patients' serum, also determine microRNA in their serum, and genomic DNA polymorphisms, the latter only at baseline. Please see next section for more detail.

To establish safety of the anti-CGRP treatment in this patient cohort, blood draw at baseline and at the 45-, 75-, 105- and 135-days of treatment time-points will also include routine systemic sentinel/surveillance markers, namely comprehensive metabolic panel and complete blood count with differential, and complete urinalysis. No more than 45 ml of blood will be collected at any given visit.

In terms of additional safety parameters, we propose an open, patient-kept side-effect log, plus home-based recordings of blood pressure, heart rate and weight at a frequency of 2x/week.

We will set up a data and safety monitoring board for proper management and oversight of data handling and patient safety-related issue; see next section.

[figure not shown]
We expect to observe effective treatment, at least in a significant subgroup of patients. Effectiveness of treatment, also magnitude of any observed therapeutic effect will be correlated with the pain/inflammation proteinaceous, lipid and RNA-based biomarkers in patients' serum, also with any polymorphisms in the patients' genomic DNA.

We also expect galcanezumab treatment to show another record of safe treatment, our expectation sculpted by analysis of in-depth data from treatment of migraineurs. Yet we will remain vigilant and implement the proposed safety sentinel measures in order not to miss adverse effects. This appears prudent because trigeminal or glossopharyngeal nerve pain plus small-fiber neuropathy is a different underlying disorder than migraine, likely representing a higher prevalence in peri-menopausal female patients. We also believe it is likely that level of chronic pain suffering-associated stress will be higher in our study population than in migraineurs.

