Patients will be recruited via the PI's clinics at Duke University, the Duke Clinics that typically refer to her attention and outside clinics and providers that refer to her as well, and DEDUCE database. In case of slow recruitment patient self-help and patient advocacy associations in the facial pain arena will be informed of the ongoing study to assist with recruitment. These organizations (Facial Pain Research Foundations, Facial Pain Association) are well-known to the PI.

11) Brief Statistical Analysis Plan

Only patients who complete the study will be included in the statistical analysis.

Response to treatment will be assessed by comparing pain metrics during the 90-day treatment period vs averaged 30 day "run-in". Outcome variables will consist of selected readout parameters of "pain metrics", namely pain subjective rating on VAS (0-10) and medication co-use. Additional outcome variables include circadian rhythm-associated metrics. A daily readout for each variable will be entered into their log by each patient, or by automatic activity reads from their motion tracking device. In similar manner, we will compare pain metrics during the 90-day treatment period vs 60-day post-treatment observation.

We intend to conduct the study with an n=20 patients to successfully complete the study. This selected number appears the most feasible and practicable number. We are confident that with an n=20 we will be in a position to do justice to the objective of initial assessment of the safety of galcanezumab in the condition under study, trigeminal or glossopharyngeal pain in the context of painful small fiber neuropathy/fibromyalgia.

Following completion of the study, we will have estimates of effect sizes and corresponding 95% confidence intervals providing information on the precision of the statistical estimates of treatment effect. Power analysis will be performed based on these estimates and will provide us with guidance for sample sizes of follow-up studies that aim for demonstrating effectiveness.

The statistical analysis will be based on a linear mixed model for repeated measures. The

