time course of pain metrics reported during the treatment period will be compared with metrics during the run-in baseline. The covariance matrix describing the nature of correlations between repeated measures will be selected based on Akaike information criterion and Bayesian information criterion, as guided by our statistics software, SAS/STAT15.1. p-values <0.05 will be considered statistically significant. Effects of treatments will be investigated with the introduction of treatment as a binary covariate (we will evaluate the effects of pre- and post-treatment in two different models).

Patients' anti-pain treatment response will be correlated with blood markers for pain, inflammation and miRNA, and also for genomic markers. This approach will be pursued in order to identify candidate biomarkers that pre-dispose patients to experience an effective or non-effective treatment response. In case of recording any particular safety-related parameters, correlation of these markers to safety metrics will also be conducted. Association between molecular biomarkers and pain- and activity-related metrics will be evaluated (i) at each time point separately using a linear regression model; (ii) by modeling the association across all time points and including time covariate in the linear regression model. The ensemble of these approaches will help determine the periods when pain or activity-related metrics and molecular markers co-evolve and become highly correlated.

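### The search for markers that predispose to response is not limited to pre-dose serum and does not adjust for run-in pain, so correlates of relief or of baseline severity can enter the candidate list

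*Combined protocol and SAP*

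**What the plan says.** Section 11 describes the analysis in general terms: "Patients' anti-pain treatment response will be correlated with blood markers for pain, inflammation and miRNA, and also for genomic markers". The next sentence gives the aim: "This approach will be pursued in order to identify candidate biomarkers that pre-dispose patients to experience an effective or non-effective treatment response". Study Design / Overview puts it similarly: "also magnitude of any observed therapeutic effect will be correlated with the pain/inflammation proteinaceous, lipid and RNA-based biomarkers", and adds DNA polymorphisms. Section 2 (Blood draw: detailed analysis) is the most open. After high responders and low or non-responders are identified, their response patterns are to be compared with every biomarker measured.

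Serum timing is in Study Design / Overview: "we intend to draw blood before treatment and at the 45-, 75-, 105- and 135-day of treatment time-points". That is one pre-dose sample and four later ones. Genomic DNA is taken at baseline only.

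Response is a comparison with the run-in: "Response to treatment will be assessed by comparing pain metrics during the 90-day treatment period vs averaged 30 day" run-in.

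Section 11 then lists two regressions of pain and activity metrics on molecular markers, "i) at each time point separately using a linear regression model" and "ii) by modeling the association across all time points and including time covariate in the linear regression model". It closes by saying that the set of approaches "will help determine the periods when pain or activity-related metrics and molecular markers co-evolve and become highly correlated". Time is the only covariate named. No passage reserves the pre-dose serum sample for the predisposition question, and none puts run-in pain in a marker model.

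**The concern.** Predisposition is a property that a patient has before treatment. Two kinds of marker can look predisposing without being so.

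- **Post-dose serum markers.** The protocol expects treatment to change them: improvement of serum inflammation markers is a secondary objective, and CGRP, the drug's target, is one of the 39 listed analytes. A later sample that correlates with response may show the consequence of relief or of the drug.
- **Pre-dose severity markers.** Because response is measured against run-in pain, run-in pain is part of the response. If relief is roughly proportional, or if there is regression to the mean, patients with more run-in pain show larger falls. A marker that tracks severity then correlates with the fall.

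The protocol hopes that the study will guide larger controlled trials and possibly a personalized-medicine approach. A candidate list that mixes consequences of relief, severity markers and real predictors is a poor start for that. The bias adds to the chance findings already to be expected from 39 analytes and more than 2000 miRNAs in 20 patients.

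**Working it through.** **Figure in the plan.** There is none to reproduce for this analysis. The n=20 is set by feasibility.

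**Inputs from the documents.** n=20 completers; significance at p<0.05 (two-sided assumed); 1 pre-dose and 4 later serum draws; response measured against run-in; 0–10 VAS.

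**Assumed inputs, not in the documents.** Run-in VAS mean 6, SD 1.5; relief a common fraction q of 10–50%; noise SD e of 1–2; marker–pain correlation ρ of 0.3–0.7. Each setting used 20,000 simulated trials.

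**Threshold.** At n=20 the critical t on 18 df is 2.101, so |r| must reach 2.101/√(18 + 2.101²) = 0.444.

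**Step 1: pre-dose marker of severity only.** Fall = q × run-in + noise, and the marker relates only to run-in VAS. Then

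corr(marker, fall) = ρ · 1.5q / √((1.5q)² + e²).

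- q=0.3, e=1, ρ=0.5: 0.5 × 0.45/√(0.2025 + 1) = 0.5 × 0.410 = 0.205.
- q=0.5, e=1, ρ=0.7: 0.7 × 0.75/√(0.5625 + 1) = 0.7 × 0.600 = 0.420.

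Share of trials in which the marker is significant:

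| Relief, noise SD | ρ=0.3 | ρ=0.5 | ρ=0.7 |
|---|---|---|---|
| 30%, 1 | 8% | 14% | 24% |
| 50%, 1 | 12% | 26% | 47% |
| 30%, 2 | 6% | 8% | 10% |
| 50%, 2 | 7% | 12% | 19% |

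At 10% relief the range is 5–8%. If response is percent fall, it is 5–8% throughout. With run-in VAS in the model it is about 5% in every setting.

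**Step 2: cross-check with a different model.** Let r be the correlation of run-in with on-treatment pain and s the ratio of on-treatment to run-in SD. Then

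corr(marker, change) = ρ(rs − 1)/√(1 + s² − 2rs).

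With r=0.5, s=1, ρ=0.5 this is 0.5 × (−0.5)/1 = −0.25, significant in 19% of trials. Over r and ρ of 0.3–0.7 the range is 8–46% at s=1 and 5–27% at s=1.3. It is about 5% after adjustment.

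**Step 3: post-dose marker that only follows current pain.** In the Step 1 model, on-treatment pain has SD_f = √((1.5(1−q))² + e²), and

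corr(marker, fall) = ρ · (q(1−q)·1.5² − e²) / (SD_f · √((1.5q)² + e²)).

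- q=0.3, e=2, ρ=0.7: 0.7 × (0.4725 − 4)/(2.259 × 2.050) = −0.533.
- q=0.3, e=1, ρ=0.5: 0.5 × (0.4725 − 1)/(1.450 × 1.097) = −0.166.

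Over all settings such a marker is significant in about 6–74% of trials, unadjusted.

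**Step 4: does adjustment alone cure Step 3?** No. For q=0.3, e=1, ρ=0.5, the partial correlation given run-in has size (ρe/SD_f)/√((ρe/SD_f)² + 1 − ρ²). With ρe/SD_f = 0.5/1.450 = 0.345, this is 0.345/√(0.119 + 0.75) = 0.370, larger than the unadjusted 0.166. In the Step 2 model (s=1), a post-dose marker adjusted for run-in is significant in 15–93% of trials, and in 50% at r=0.5, ρ=0.5. The restriction to pre-dose samples and the covariate are both needed.

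**The case against.** The strongest reply is that section 11 keeps two aims in separate sentences. The regressions at each time point and across time points are tied to finding when markers and pain move together. A reader might infer that they are the predisposition models and therefore wrongly built. The text does not support that. They suit the co-evolution aim, and the baseline time point is among them. What remains is that the predisposition sentence itself names no sampling time and no covariate, and that section 2 opens the comparison to every biomarker measured.

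A second reply is that the idea of predisposition already implies the pre-dose sample, so silence is not commitment to a wrong analysis. This is fair as far as it goes, but four of the five draws would be eligible as written. Even on the favourable reading, run-in pain is still missing.

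A third reply concerns size, and it stands. The inflation in Step 1 depends on absolute fall, sizeable proportional relief and modest noise. Section 11 does not say whether an individual's response is absolute or percent, and its pain metrics include medication use. With percent fall or little relief, the severity bias nearly vanishes.

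Finally, this is an open-label pilot whose primary criterion is safety, and the markers are called candidates. No multiplicity control is stated, and 2000 × 0.05 = about 100 miRNAs per time point would be significant by chance. The fix does not touch that. It limits the importance of the point but does not remove a systematic bias that is nearly free to avoid.

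**Conclusion.** The concern holds in a limited form. As written, the plan allows post-dose serum levels and unadjusted severity markers to be reported as predisposing to response. A reader might infer that such markers will pass as predictors. The documents support only that they can. The rate for a pure severity marker is about 5–47% unadjusted on absolute fall (5–8% on percent fall) against about 5% adjusted. For a post-dose marker that follows current pain it is about 6–74%. Every SD, correlation and relief fraction behind these ranges is an assumption.

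A reader might also extend the post-dose problem to the genomic markers. It does not apply there, because DNA is baseline-only. The severity problem can still apply to genotype if it is related to run-in pain.

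Day 135 is described as a day of treatment although treatment lasts 90 days. This does not affect the conclusion: counted from the first dose, or from the start of a 30-day run-in (45 − 30 = 15 days after the first dose for the earliest draw), all four later draws are post-dose.

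The point is a cheap improvement to an exploratory secondary objective. It does not threaten the safety or main pain analyses.

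**What to change.** In section 11, separate the two questions, and align section 2 and Study Design / Overview with the result.

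1. **Predisposition.** Regress mean treatment-period VAS on the pre-dose marker, or on genotype, with the patient's run-in mean VAS as a covariate. Use no post-dose samples.
2. **Markers accompanying response.** Keep the regressions at each time point and across time points for the co-evolution aim. Label every post-dose association as accompanying response, not predicting it.
3. **Limit of the design.** State that without a control arm, markers found under item 1 may be prognostic and not specific to galcanezumab.

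The cost is a change of wording, since all the data are already to be collected. The model spends one degree of freedom on run-in VAS, and post-dose samples no longer feed the list of predictors.

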Treatment with a CGRP-neutralizing antibody, galcanezumab in this specific patient group, being seen in the PI's clinics on a regular basis, is rooted in the rationale of unmistakable presence of clinical signs of neurogenic inflammation in the painful territory, such as episodic swelling combined with redness/hyperemia, also relief by external cold application which typically patients with trigeminal or glossopharyngeal nerve pain abhor.

Primary Outcome Measures

Primary criterion is to establish an excellent safety profile that recapitulates the favorable data recorded in migraineurs. The primary pain-related objective is reduction of pain and reduced use of rescue and other anti-pain medication.

Inclusion Criteria

- G50.1 diagnosis (can encompass an add-on G50.0 and other headache G43.... codes), or G52.1 diagnosis code (with explicit mentioning of pain of glossopharyngeal origin) **AND** small fiber neuropathy diagnostic codes G63.3, G60.8, G62.8 (can encompass fibromyalgia diagnostic code M79.7)
- 18-80 years old
- not allergic to galcanezumab and other hu mAb biologics

Exclusion Criteria

- allergic to galcanezumab and other hu mAb biologics
- pregnancy

Study Design / Overview

We propose to treat patients open label for 12 weeks, with galcanezumab, supplied by Eli Lilly, as add-on to all other therapeutic measures. We propose to use a 240mg/120mg/120mg regime, with subcutaneous (self-)injections every 4 weeks.

To reflect pain experienced by patients, the primary read-out is pain level on a 0-10 visual analog scale. We will be prompting patients to record a daily summary read at the end of each day.

[figure not shown]
The second criterion is reduction of intake of anti-pain medication (rescue PRN or regular) which the patients will record.

Chronic pain, especially fibromyalgia pain combined with trigeminal or glossopharyngeal nerve pain, is a potent disruptor of circadian rhythm. We strongly believe that this is an important and hitherto under-appreciated contributor to individual disease burden. Therefore, the third criterion is assessment of circadian rhythm function. We will assess this by having the patient rate subjectively how energetic they feel during awake day-time. Wearable activity monitors will be used to address how many hours patients sleep per

24h period, with detailed focus on total duration of sleep/rest and duration of night-time sleep only.

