We also expect that the proposed studies will be very important for guiding future, more in-depth studies involving larger patient cohorts, placebo-controlled/double-blinded studies, which will possibly lead us toward a personalized-medicine approach.

Study Design Detail

1) Schedule of Activities over Time

2) Blood draw: detailed analysis

Before treatment, and at 45th, 75th, 105th and 135th day of treatment, we propose to assess the following blood parameters, related to pain-associated biomarkers in the systemic circulation.

For this, we propose to study cytokine/chemokine pain- and inflammation markers in patients' serum, using commercially available protein multiplex detection assays. In serum, the following 39 cytokines/chemokines/lipid mediators/peptides will be measured: EPO, GM-CSF, IFN- γ , IL-1 β , IL-2, IL-4, IL-5, IL-6, IL-9, IL-10, IL-12/IL-23p40, IL-12p70, IL-13, IL-15, IL-16, IL-17A, IL-17A/F, IL-17C, IL-17E/IL-25, IL-17F, IL-21, IL-22, IL-23, IL-27p28/IL-30, IL-31, IL-33, IP-10, KC/GRO, MCP-1, MIP-1 α , MIP-1 β , MIP-2, MIP-3 α , TNF- α , VEGF-A, TGF- β , CGRP, Resolvin-D1, Prostaglandin-E2. For these measurements, we will be using a human 35-plex ELISA (U-PLEX Biomarkers) and single ELISAs (Signosis; Cayman).

These are key mediators and indicators of pain and inflammation. We believe it will be feasible to conduct these assays. For each marker there is sufficient evidence supporting its role in pro-algesic inflammation or organismal response to tissue damage. We are

convinced that their ensemble will prove a powerful source of mechanistic data that will elucidate treatment responses to galcanezumab in our patient population.

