Each page is intended for 1 day. For each day, they will record a summary pain rating on a visual analog scale (VAS) from 0-10. Also for each day, they will document all medications taken, listing analgesic medication first, both prescription as well as over-the-counter. On another 0-10 VAS they will rate their subjective level of how energetic they felt. They will record length of sleep, night-time and daytime.

Patients will also be wearing wearable activity monitors. In case they already have such a device, it will be used (e.g iWatch, fitbit). In case they do not have one, they will be provided with such a device, a Huawei Terra-B19 Band 3 Pro. Instructions for use will be provided.

After final data acquisition by the RMT, the Huawei device will be left to the patient for their own future use.

The d180 page of the subjective rating protocol will contain the question "*Do you want to continue using Emgality (galcanezumab) for s.c. injection?*"

Importantly, handling and acquisition of these data will not record any HIPAA-pertinent PHI because the activity monitor will not record or store any of these. The 200-page booklet will be tagged with a unique ID number in front, back and on the side of the pages, being mindful not to include any PHI.

For 2x/week measurement of blood pressure, heart rate and body weight, patients will be supplied with the following devices so that these metrics can be acquired in their domestic environment:

home scale for body-weight

blood pressure and heart rate monitoring device

5) Patient Training and Instructions

At the initial visit, patients will receive detailed instructions how to fill out the subjective rating booklet, how to self-inject, and how to wear, use and handle the activity monitors, in case they will be provided with one, or how to make sure that their own activity monitor will record activity and sleep as intended.

Training how to self-inject Emgality will be provided by the study staff. Patients will also be provided with written instructions.

It will be verified that they understand the need to record and document blood pressure, heart rate and body weight 2x/week, to be documented on their daily log page.

6) Research Management Team (RMT)

The Research Management Team will consist of Principal Investigator, Sub-Investigators, Regulatory/Data Coordinator and Research Coordinator/Research Nurse

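### The marker–pain regressions do not account for anti-inflammatory drug use before a draw; if such use is common and follows pain, the PGE2–pain association can be biased downward

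*Combined protocol and SAP*

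**What the plan says.** Study Design / Overview gives galcanezumab "as add-on to all other therapeutic measures". The Exclusion Criteria there, and the detail in section 8, concern antibody allergy and pregnancy. Neither they nor the rest of the readable text limits analgesics or asks for a hold before blood sampling.

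The same overview makes analgesic intake an outcome: "The second criterion is reduction of intake of anti-pain medication (rescue PRN or regular) which the patients will record". Under section 4, the daily booklet captures it: "they will document all medications taken, listing analgesic medication first, both prescription as well as over-the-counter".

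Section 2 lists 39 serum analytes, ending with "CGRP, Resolvin-D1, Prostaglandin-E2". They are measured at five draws: "Before treatment, and at 45th, 75th, 105th and 135th day of treatment".

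Section 11 specifies two biomarker regressions. Model (i) is "Association between molecular biomarkers and pain- and activity-related metrics will be evaluated (i) at each time point separately using a linear regression model", with no covariate named. Model (ii) proceeds "by modeling the association across all time points and including time covariate in the linear regression model". Medication co-use appears in section 11 as one of the pain metrics, that is, as an outcome. It is not named as an adjustment variable.

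**The concern.** An exposure that depends on pain and also changes the assay value confounds a regression of one on the other. PRN rescue means intake can rise with pain, and the protocol looks for intake to fall when treatment works. If some of that intake is an NSAID, part of the variation in PGE2 between patients and between visits reflects who had recently taken one.

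The direction is predictable. Patients in more pain would tend to have drug-lowered PGE2, and a patient who improves and stops an anti-inflammatory could show PGE2 rising. Both push the association downward, against the positive link that the protocol's inflammation hypothesis would lead one to expect.

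At stake are the secondary objective on serum inflammation markers and the search for candidate biomarkers of response, which are meant to guide later and larger studies. Enrolling more patients would not remove this bias.

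**Working it through.** The plan gives no figure to reproduce: n=20 is justified by feasibility, with no effect size or SD.

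**From the documents:** 20 completers; significance at p<0.05 (taken as two-sided); PGE2 measured at five draws; no medication covariate.

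**Assumed:** how many patients use an anti-inflammatory near a draw, how strongly use follows pain, and how far it lowers the marker.

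**Step 1: threshold.** At n=20, with t = 2.101 on 18 degrees of freedom, the critical correlation is |r| = t/√(18+t²) = 2.101/√22.41 = 0.444.

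**Step 2: induced correlation with no true link.** Let p be the proportion of users, dP the excess pain in users and dM the marker reduction in users, both in SD units. Then

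r = −p(1−p)·dP·dM / √{[1+p(1−p)dP²]·[1+p(1−p)dM²]}

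- p=0.3, dP=0.5, dM=0.5: −0.0525/1.0525 = −0.05; simulated rejection rate 5.7%.
- p=0.5, dP=1.0, dM=1.5: −0.375/√(1.25×1.5625) = −0.27; rejection rate 20.3%.
- dP=0 (use unrelated to pain): r=0; rejection rate about 5%.

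**Step 3: use rising with the pain score.** Assumed: VAS mean 5.5 and SD 2; log-marker residual SD 0.6; logit P(use) = b(VAS−5.5), so about 50% use overall. A log effect of −0.7 halves the marker (e^−0.7 = 0.50), and −1.2 cuts it by 70% (e^−1.2 = 0.30). Rejection rates for model (i) without adjustment, no true link:

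| Drug effect on marker | b=0.3 | b=0.5 | b=0.8 |
|---|---|---|---|
| Halved | 7.9% | 13.1% | 21.7% |
| Cut by 70% | 12.8% | 23.9% | 40.8% |

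With exposure as a covariate the rate is 4.9–5.3%.

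**Step 4: milder inputs.** With a halved marker and b=0.3, 20% use gives 7.2% and 10% use gives 5.4%. With 50% use but b=0.1, the rate is also 5.4%. A 30% reduction (log effect −0.35) gives 4.7–7.3% for b from 0.1 to 0.5.

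**Step 5: change over time.** Regressing marker change on pain change, with use falling as pain falls, gives 8–28% without adjustment (mean r −0.13 to −0.31) and 4.5–5.7% with it.

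**Step 6: a true link of r=0.5.** With no drug effect, power at n=20 is about Φ(0.549×√17 − 1.960) = Φ(0.305) = 62%. Without adjustment, detection falls as low as 4%; with the covariate it is about 47–63%. Because use is partly a consequence of pain, conditioning on it narrows the pain range within each group, so some loss remains.

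**Step 7: exposure recorded with error.** In the 70% case, 10% misclassification leaves the adjusted rate at about 7–13%, and 20% leaves it at about 8–22%.

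**The case against.** Several points on the other side stand:

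- **The drugs are not named.** The documents mention no NSAID or corticosteroid and do not say how many patients take one. These drugs are permitted only in the sense that nothing excludes them, and their action on prostaglandins is general pharmacology. The effect on the cytokines and other markers is less certain, so "may affect" is as far as one can go.
- **Medication is not ignored altogether.** It is recorded daily and analysed as a pain metric. It is missing only as a covariate, and no drug class is distinguished.
- **The upper figure is a corner of an assumed grid.** With infrequent or weakly pain-linked use, the inflation is negligible.
- **The covariate is not a complete cure.** Booklet entries are daily, and clock times are not mentioned. The schedule figure is not shown, so neither a sampling rule placed there nor the presence of booklet days before the baseline draw can be checked.
- **The work is exploratory.** With 39 analytes at five draws there are 195 tests per metric, and 195×0.05 = 9.75 would be significant by chance.

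The last point does not dispose of the matter. Chance findings have no fixed direction, whereas this bias acts on a known marker in a known direction and can also suppress a real association.

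A reader might infer that patients in more pain will show lower PGE2, or that responders will show it rising. The documents do not support either as a prediction: if inflammation drives pain, drug use may only weaken a positive association.

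**Conclusion.** The concern holds conditionally. As written, neither biomarker regression separates a drug effect on the assay from biology. If anti-inflammatory use near the draws is common and follows pain, the PGE2–pain association is biased downward. The same may apply to other inflammatory markers, with less certainty.

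The size is unknown. Under the assumed inputs, a nominal 5% test rejects in about 5% to 41% of trials with no true link. The upper end needs 50% use, strong linkage to pain and a 70% marker reduction together.

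The calculations cover markers against pain at one draw, and change against change. They do not cover a baseline marker against later response, so no size is claimed there. A reader might also infer that the whole panel, including the microRNA and exome work, is compromised; nothing in the documents supports that.

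**What to change.** In section 11, specify the following:

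1. From the booklet, derive a yes/no variable for any NSAID or systemic corticosteroid in a window before each draw (for example 3 days). Fix the window and drug list before assay results are seen. If no booklet days precede the baseline draw, use the medication history for that draw.
2. Add this variable as a covariate in regressions (i) and (ii) for PGE2. For the other inflammatory protein and lipid markers, add it as a sensitivity analysis.
3. Report PGE2 change also among patients with the same exposure status at both draws.
4. Where the pain metric is medication co-use itself, state that an association with PGE2 may be a direct drug effect.
5. Report the proportion exposed at each draw, so that readers can judge how much the adjustment matters, and label the results exploratory.

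The cost is plan wording, one derived variable and one degree of freedom per model. The same-status subset will be smaller than 20, and misclassified exposure leaves residual bias. No medication is restricted, and no visit or sample changes.
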